3.6.1. Adverse events

Definition:

- **Emergent Adverse Events (EAE)** during the double-blind (*resp. open-label, combined*) period are defined as all adverse events which occur in the period #1 (*resp. #3, #5*) (as per table above), or which started strictly before period #1 (*resp. #3, #5*) but which worsen (in terms of intensity) or become serious according to the investigator opinion during period #1 (*resp. #3, #5*).
- **Treatment Emergent Adverse Events (TEAE)** during the double-blind (*resp. open-label, combined*) period are defined as all adverse events which occur in the period #2 (*resp. #4, #6*) (as per table above), or which started strictly before period #2 (*resp. #4, #6*) but which worsen (in terms of intensity) or become serious according to the investigator opinion during period #2 (*resp. #4, #6*).
- **AE starting during the run-in period** are defined as all adverse events which started strictly before period #1.

Analyses:

Number of events as well as number, percentage and annual incidence rate of patients reporting at least one event, presented by primary System Organ Class (SOC), and Preferred Term (PT), will be provided for:

- Serious EAE and deaths for period #1, #3 and #5.
- TEAE, TEAE leading to IMP withdrawal, TEAE requiring new treatment or increase of ongoing treatment, TEAE requiring surgical or medical procedure, TEAE related to IMP, serious TEAE, severe TEAE, non-serious TEAE for periods #2, #4 and #6.

TEAE will be described according to the seriousness, the intensity, the relationship with the IMP, the action taken regarding the IMP, the requirement of added therapy and the outcome.

Moreover, TEAE, TEAE related to IMP and serious TEAE will be presented according to their time to onset in weeks calculated from the start of the period #2 (*resp. #4 and #6*).

AE starting during the run-in period will be also described by SOC and PT in the SS.

All adverse events reported after the last Bumetanide intake + 2 days (excluded) will be listed. All COVID-19 infection reported during the study will be listed.

Number of events as well as number, percentage of patients reporting at least one event, presented by primary System Organ Class (SOC), and Preferred Term (PT), will be provided for all AE and all serious AE occurring after the first intake in the extension part in the patients included in the extension period.

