8.9.3. Responsibilities of the sponsor

In accordance with international guidances, the assessment of the seriousness and the causality of adverse events are usually made by the investigator but falls also under sponsor's duties, who is responsible for ensuring that all suspected unexpected serious adverse reactions are reported to Competent Authorities and Ethics Committees.

The sponsor will review the seriousness of the adverse events and the causality of (at least) the serious adverse events, whether reported by the investigator or upgraded by the sponsor. The causality and the seriousness may be upgraded (but never downgraded). Anonymized copies of documents providing useful information such as reports of further consultations, laboratory tests reports, reports of other examination aiding diagnosis may be asked for the event assessment. If the assessments of the investigator and the sponsor are different, both will be reported in the clinical study report.

In addition, the sponsor is responsible for determining whether an AE is **expected or unexpected**. An AE will be considered unexpected if the nature, severity, or frequency of the event is not consistent with the risk information previously described for the IMP.

Independently of the regulatory obligations of the investigator, the sponsor must report the pharmacovigilance data to the appropriate Authorities and to all the investigators involved, according to the requirements stated in ICH Good Clinical Practice guidelines and local regulations.

In case of any new safety information (likely to affect the Benefit/Risk balance of the product), the sponsor will inform all investigators involved in any study with the same drug that this new safety information has been reported.

As a result, study participants will be informed via his/her respective investigator of this new safety information and will receive a revised informed consent to be signed as described in section 13.3 of the protocol 'Modification of the information and consent form'.

The concerned Authorities will be notified as soon as possible by the sponsor of the Data Monitoring Committee (DMC) recommendations if any, where relevant for the safety of subjects (i.e. modification or termination of the study).

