10.2.2.6. Safety analysis

10.2.2.6.1. Adverse events

Double-blind treatment period:

Number of events, number and percentage of patients reporting at least one event, presented by primary system organ class, and preferred term will be provided for serious adverse events and emergent adverse events under treatment during the double-blind treatment period in the Safety Set.

Emergent adverse events will be described according to the seriousness, the intensity, the relationship, the action taken regarding the IMP, the requirement of added therapy, and the outcome.

Of note, the seriousness and the relationship to the IMP of the adverse event correspond to the investigator opinion or, in case of events upgraded by the sponsor for seriousness or for causality in case of SAE, to the sponsor opinion.

Open-label active treatment period:

The same analysis will be performed for adverse events occurred or worsened during the open-label active treatment period in the Safety Set.

Post-treatment period:

All adverse events reported after the last study drug intake will be listed.

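### SAP 3.6.1 lets only the investigator's view of seriousness make an earlier-onset event emergent, while the protocol also uses sponsor upgrades; the effect is narrow

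*SAP*

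**What the plan says.** **Protocol, seriousness in the analysis.** Section 10.2.2.6.1 says that seriousness and relationship to the study drug follow the investigator or, "in case of events upgraded by the sponsor for seriousness or for causality in case of SAE, to the sponsor opinion". Section 8.9.3 lets the sponsor raise either assessment but never lower it, and has both opinions reported in the clinical study report when they differ.

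**Protocol, what is tabulated.** For the double-blind period, the tables "will be provided for serious adverse events and emergent adverse events under treatment during the double-blind treatment period in the Safety Set". For open label: "The same analysis will be performed for adverse events occurred or worsened during the open-label active treatment period in the Safety Set". Emergent is not defined further.

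**SAP, emergence.** Section 3.6.1 defines emergent adverse events (EAE) and treatment-emergent adverse events (TEAE) in parallel. An event qualifies by onset, since EAE "are defined as all adverse events which occur in the period #1" (or the matching later period). An event with earlier onset qualifies only if it is one of those "which worsen (in terms of intensity) or become serious according to the investigator opinion". Both definitions carry this wording.

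**SAP, outputs.** The serious-event tables are limited to emergent events, for example "Serious EAE and deaths for period #1, #3 and #5", with serious TEAE for periods #2, #4 and #6. Run-in events have their own output: "AE starting during the run-in period will be also described by SOC and PT in the SS". No split by seriousness is stated there. The supplied SAP text does not mention sponsor upgrades, and its visible entry for version 3.0 lists no change on this point.

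**The concern.** For seriousness the protocol recognises two assessors. The SAP names one of them at the point where seriousness decides whether an earlier-onset event enters a period's tables. This is a stated narrower rule, not an omission, and a programmer would code it as written.

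An ongoing event that turns serious need not get a new onset date. Protocol 8.9.2.2 has a change in seriousness recorded on the page already opened for that event. The SAP's seriousness route exists for exactly this situation. If only the sponsor judges that the event became serious, the route is closed. The study report could then describe a sponsor-upgraded serious event that the serious emergent tables for that period do not contain.

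**Working it through.** No event count, rate or sample size enters, so this is a check of logic, not arithmetic.

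**Step 1. Inputs.** The seriousness rule is from protocol 10.2.2.6.1, the upgrade-only rule from protocol 8.9.3, the emergence rule from SAP 3.6.1, the period boundaries from SAP Table (3.6) 1, and the recording of pre-treatment events from protocol 8.9.1.

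**Step 2. Cases.** Take an event that is serious only because the sponsor upgraded it.

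| Onset | Intensity worsened in the period | Emergent under SAP 3.6.1 | Emergent if upgrades count |
|---|---|---|---|
| In the period | Yes | Yes | Yes |
| In the period | No | Yes | Yes |
| Before the period | Yes | Yes | Yes |
| Before the period | No | **No** | Yes |

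One of four logical cases drops out. That is a count of cases, not a frequency.

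**Step 3. Which events fall in the fourth case, by period.**
- *Double-blind (#1, #2), both arms.* The period starts at the first double-blind intake, so only run-in events can be affected. Protocol 8.9.1 records a pre-treatment event as an adverse event only if it is associated with a study procedure or condition. Otherwise it goes to medical history.
- *Combined (#5, #6), S95008/S95008 arm.* The start is the same, so again only run-in events are affected. Events that began in the double-blind period are already emergent by onset.
- *Open label (#3, #4), Placebo/S95008 arm.* The period starts at the first open-label intake, so any event that began before it can be affected.

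**Step 4. Where the omitted event still appears.**
- *Run-in onset:* in the run-in table.
- *Double-blind onset, placebo patient:* emergent in period #1 by onset, so missing only from the open-label tables.
- *Onset in a gap between the end of double-blind and the first open-label intake, placebo patient:* by onset it lies in neither #1 nor #3, and the run-in table stops before #1. The separate safety listing in SAP 3.6 is for delays above 30 days. The listing of events after the last bumetanide intake plus 2 days does not reach this gap, because these patients have not yet taken bumetanide. With a shorter delay, no EAE table contains the event. SAP 2.1 and 3.2.1 both anticipate such delays.

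**The case against.** **The protocol sentence is about attribution, not emergence.** It says whose opinion fills the seriousness and relationship fields. It does not define emergence for the double-blind period, and the open-label rule has no seriousness route at all. This stands. A reader might infer that the SAP count of serious events can only equal or fall below the protocol's. The documents do not support that. An earlier-onset event that the investigator judges to have become serious, with unchanged intensity, is emergent in open label under the SAP but not clearly so under the protocol. In that respect the SAP is the wider of the two.

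**The serious and related tables.** A reader might also infer that sponsor upgrades are lost from the serious TEAE and drug-related tables generally. The investigator-only phrase qualifies the emergence route alone. On whose opinion fills those tables the SAP is silent, and SAP section 1 says that it follows the main features of the amended protocol. The protocol rule therefore remains in force, and restating it would be a clarification.

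**Upgrades do not vanish.** Protocol 8.9.3 has both opinions reported when they differ. That is real mitigation, although it does not put the event into the tables.

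**Dating.** The route needs the event to become serious within a dated period, and protocol 8.9.3 gives no date for a sponsor's upgrade. If the review date were used, an unchanged run-in event could be labelled treatment-emergent merely because of when it was reviewed. This stands too, and the fix has to deal with it.

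None of this removes the central fact: where seriousness alone decides entry, the SAP admits one assessor and the protocol's analysis rule admits two.

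**Conclusion.** The point holds in a narrow form. An event that began before the period, did not worsen in intensity, and is serious only by sponsor upgrade is absent from that period's serious EAE and TEAE tables. In the randomised comparison this can concern only run-in adverse events linked to a study procedure or condition. Otherwise it concerns the single-arm open-label tables for patients who started on placebo.

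The number affected is probably zero or very few. That is a judgement from how many conditions must coincide, because the documents give no upgrade rate and no expected count of serious events. A reader might take five serious events in an arm, suppose one is omitted, and infer a 20% undercount (1/5). Neither figure comes from the documents, so no percentage should be attached. Events with onset in the period or with worsened intensity are unaffected, as are all efficacy analyses. The conclusion assumes that the SAP wording is programmed literally. It is a minor point, worth correcting because the correction is almost free.

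**What to change.** In both the EAE and TEAE definitions of SAP 3.6.1, replace the investigator-only condition with: *is judged to have become serious by the investigator or, where the sponsor has upgraded the event, by the sponsor*. Add: *the event is assigned to the period in which the change that made it serious occurred, not to the date of the sponsor's review*.

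Optionally, restate in the same section the protocol 10.2.2.6.1 rule: sponsor upgrades apply to seriousness and, for serious events, to relationship, in the serious and related tables. This is clarification only.

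The cost is SAP wording and a small programming change. The sponsor's assessment already exists under protocol 8.9.3. The one practical requirement is that, for upgraded events, the date of the underlying change can be identified from the event record.

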3.3.2. Concomitant treatments and therapies

All specific (resp. non-specific) concomitant treatments taken at inclusion, during the double-blind (resp. open-label, combined) period, at the first IMP intake of the open-label period and after the last IMP intake of the double-blind (resp. open-label) period will be described in the SS (SSO when open-label and SSC when combined), by ATC code. Therapies for autism spectrum disorder will also be described at inclusion and during the double-blind period in the SS and during the open-label in the SSO and during the combined period in the SSC. The number and percentage of patients with at least one therapy of ASD will be described overall and by type of therapy at inclusion in the SS. The number and percentage of patients with at least one new added therapy / one modification in current therapy / one clinically relevant modification in therapy will be described overall and by type of therapy in each period.

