3.6. Safety analysis

All safety analyses will be performed on the taken treatment at W000 as following:

- For the double-blind period in the SS by treatment group (S95008 vs placebo).
- For the open-label period: in the SSO on the Placebo/S95008 arm.
- For the combined period: in the SSC on the S95008/S95008 arm.

Six periods are of interest to present accurately the safety endpoints. The start and end date of these periods are summarized in the following table:

Table (3.6) 1 - Definition of periods of emergence for safety events

| Period ID | ANALYSIS PERIOD | START | END |
|------------------|--|--|--|
| #1 | Emergent during the double-blind period | First intake in double-blind | End of double-blind period (including W26) |
| #2 | Treatment Emergent during the double-blind period | First intake in double-blind | Min(Last intake in double-blind + 2 days, First intake in open-label) |
| #3 | Emergent during the open-label period | First intake in open-label (W26 not included) | End of open-label period (including W52 and follow-up) |
| #4 | Treatment Emergent during the open-label period | First intake in open-label (W26 not included) | Last intake in open-label + 2 days (included) |
| #5 | Emergent from the combined period | First intake in double-blind | End of open-label period (including W52 and follow-up) |
| #6 | Treatment Emergent from the combined period | First intake in double-blind | Last intake in open-label + 2 days (included) |

Listing of main safety data (including adverse events) and start/end date of each period will be provided for:

- Patients who had a delay superior to 30 days between the double-blind and the open-label period will be listed separately.

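### SAP 3.6.1 ties the late adverse event listing to the last bumetanide intake instead of the last study drug intake, so placebo children who never take open-label drug have no listing rule

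*SAP*

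**What the plan says.** **Protocol 10.2.2.6.1**, on the post-treatment period: "All adverse events reported after the last study drug intake will be listed". This applies to either arm.

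**SAP 3.6.1**: "All adverse events reported after the last Bumetanide intake + 2 days (excluded) will be listed". The next sentence adds "All COVID-19 infection reported during the study will be listed".

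**SAP 3.6, Table (3.6) 1.** Period #1 (emergent, double-blind) runs to "End of double-blind period (including W26)". Period #2 (treatment-emergent, double-blind) runs to "Min(Last intake in double-blind + 2 days, First intake in open-label)". Periods #3 and #5 run to "End of open-label period (including W52 and follow-up)".

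**SAP 3.6.1, tables.** The emergent periods are tabulated only for "Serious EAE and deaths for period #1, #3 and #5". All other event tables, including the one for non-serious events, use the treatment-emergent periods #2, #4 and #6.

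**SAP 3.3.2** uses a treatment-neutral anchor for concomitant treatments: those taken "after the last IMP intake of the double-blind (resp. open-label) period will be described in the SS".

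**Follow-up off drug.** Protocol 5.6.1 says that stopping IMP in the double-blind period is not study withdrawal. Protocol 8.9.1 extends the adverse event reporting rules to children who stop the drug and stay in the study.

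**The concern.** Placebo children can receive bumetanide only from W026, in the open-label period. A placebo child who never reaches that period has no last bumetanide intake, so the SAP sentence cannot be applied to that child. A bumetanide child who stops on the same day has such a date, and later events are listed.

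The late-event listing would therefore depend on the arm. A reader who saw off-drug events after bumetanide and none after placebo could take the difference as real when it came only from the listing rule. There is also an internal mismatch: under SAP 3.3.2, a medicine given for such an event in a placebo child would be described, but the event itself would not be listed.

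**Working it through.** The plan gives no figure for this listing, so the check is mainly textual.

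**1. Who is covered by each rule**

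| Child | Last study drug is bumetanide? | Protocol rule | SAP rule, read literally |
|---|---|---|---|
| Bumetanide arm, stops in double-blind | yes | listed | listed |
| Bumetanide arm, goes on to open label | yes | listed | listed |
| Placebo arm, goes on to open label | yes | listed | listed |
| Placebo arm, stops in double-blind, no open-label dose | no | listed | no anchor date |
| Placebo arm, completes double-blind, no open-label dose | no | listed | no anchor date |

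The SAP's 2-day tail loses nothing in itself, because events in those 2 days fall in the treatment-emergent window.

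**2. Does another output in the SAP text catch a non-serious event in the last two rows, starting more than 2 days after the last dose?**

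- Treatment-emergent tables, period #2: no. The window closes 2 days after the last double-blind dose.
- Periods #4 and #6: no. Both need open-label intake.
- Period #1 tables: no. They hold serious events and deaths only.
- Listing for children with more than 30 days between the two periods: no. These children never start the second.
- COVID-19 listing: only if the event is a COVID-19 infection.

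**3. How long the uncovered time can be**

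Nominal days: W026 = 182, and the stop visits followed by a W026 visit in Protocol Table (4.2.2) 2 are days 17, 28, 56, 84 and 112. Assume that the last dose is on the day of the stop visit and that the child is followed to W026. Days inside period #1 but outside period #2 = 182 − stop day − 2.

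| Stop visit | Calculation | Days | Share of 182 |
|---|---|---|---|
| D017 | 182 − 17 − 2 | 163 | 89.6% |
| W004 | 182 − 28 − 2 | 152 | 83.5% |
| W008 | 182 − 56 − 2 | 124 | 68.1% |
| W012 | 182 − 84 − 2 | 96 | 52.7% |
| W016 | 182 − 112 − 2 | 68 | 37.4% |

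These are maxima. Protocol 4.2.2 and 5.6.1 keep the W012 and W026 assessments only for children whose background care is not importantly changed.

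**4. Wend, 6 weeks (42 days) after the IMP stop**

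- Stop at W020: 140 + 42 = day 182, nominally still within period #1, so serious events are tabulated by arm.
- Stop at W026: 182 + 42 = day 224. After the 2-day tail this leaves days 185 to 224, which is 42 − 2 = 40 days. If period #1 ends at W026, a placebo child who does not continue has neither a table nor a listing rule for these days.

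**5. How many children**

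The documents do not say. The sample size section assumes about 15% premature withdrawal with about 100 children per arm. If that were equal in the arms and all of it were IMP stops, it would be 100 × 0.15 = 15 placebo children (5 to 20 for rates of 5% to 20%). Placebo completers who decline open label would add to this, and children who leave the study at once would contribute almost nothing. No event count follows.

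**The case against.** The best defence is that the word is a slip. The SAP states that it accords with the main characteristics of the amended protocol, whose rule covers both arms. The design expects every child to end on bumetanide, so for most children the two anchors are the same date. No text states an intention to treat the arms differently, and the templates may already follow the protocol. This is probably right about intent. It does not settle the wording, because the SAP separates the two terms elsewhere: in 2.1 the Safety Set needs a dose of IMP while the open-label sets need a dose of bumetanide, and 3.3.2 speaks of the last IMP intake. A programmer who follows the SAP's own vocabulary would leave these children out.

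It is also fair to say that a by-patient listing is not an arm comparison, so any misreading is a possibility and not a demonstrated harm.

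Three stronger readings are tempting, and the documents do not support them:

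- *That the SAP is wrong to have no between-arm table of all emergent events for period #1.* Protocol 10.2.2.6.1 itself tabulates non-serious events only under treatment and lists the rest. A 2-day tail also fits the short duration of action stated in SAP 3.4.2.1. Such a table is a preference.
- *That serious events are lost.* Up to W026 they are tabulated by arm, on or off drug. Beyond W026 the gap needs a placebo child who stops at W026 without continuing, and a period #1 that ends there. SAP 3.1.2 leaves the exact stop dates to be specified.
- *That up to 90% of the double-blind period goes unreported.* That is the ceiling on calendar time for one early stopper. It is not a loss of events.

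**Conclusion.** The concern holds as a minor departure from the protocol. SAP 3.6.1 narrows a rule that covers both arms to one that, read literally, excludes placebo children who never take open-label bumetanide. Their non-serious events from the third day off drug have no place in the SAP text, COVID-19 infections excepted.

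The size in events is unknown and may be near zero; it is nil if the listing is programmed as the protocol says. The primary analysis, the treatment-emergent tables, and serious events and deaths to W026 do not change.

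The conclusion rests on a literal reading of the sentence and on the SAP text alone. For early stoppers it also rests on an inference from the discontinuation schedule that a child who definitively stops IMP does not enter open label; no document says so outright.

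**What to change.** In the SAP 3.6.1 sentence, replace bumetanide with study drug (IMP), keep the 2-day tail, and add that the listing shows the arm received at W000. Check that the listing template agrees. This restores the protocol rule. It also covers events up to Wend in placebo children who stop at W026 and do not continue, wherever period #1 is finally set to end.

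The cost is one phrase and a check of one listing program, on data already collected.

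One small case stays outside the new wording: a placebo child with a gap of 3 to 30 days before open label. A non-serious event in that gap comes before the last study drug intake, so the protocol's rule does not list it either; the same event in a bumetanide child falls in period #6. A line in the listing specification could include it.

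A supplementary period #1 table of all emergent events by arm is optional. It would mix on-drug and off-drug time, with care after the stop left to the physician, so it should not displace the treatment-emergent tables.
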